5.2.2 Replacement Participants

Participants in the IV portion of this study who are unable to provide at least 3 timed PK samples may be replaced.

5.2.3 Reasons for Participant Withdrawal

A participant or his/her parent/guardian may voluntarily discontinue participation in this study at any time. The investigator may also, at his/her discretion, discontinue the participant from participating in this study at any time. Participants may be prematurely discontinued from the study for any of the following reasons:

- Participant or investigator noncompliance with the study protocol
- At the request of the participant, investigator, treating physician, or sponsor
- Adverse reaction or suspected adverse reaction.

Participants are not obligated to state the reason for withdrawal. The reasons for withdrawal, or failure to provide a reason, must be documented by the investigator on the completion/ withdrawal section of the CRF. The participant who withdraws early or is withdrawn early will be requested to complete end-of-study safety evaluations, and will be provided appropriate care under medical supervision until the symptoms of any adverse event (AE) resolve or the participant's condition becomes stable. Participants withdrawn from the study due to an AE must be followed per protocol (see **Section 8.2.4**).

5.2.4 Termination of Study

This study may be terminated at any time by NICHHD, the Investigational New Drug Application (IND) sponsor, or the Data Monitoring Committee (DMC) if serious adverse reactions occur in 2 or more participants that are directly related to study drug, or if, in NICHHD's judgment, there are no further benefits to be achieved from the study. A study site may be terminated if the investigator does not adhere to the study protocol.

6 STUDY PROCEDURES

6.1 Summary of Procedures

See the schedule of study events and procedures (**Table 1**).

1. Medical history will be obtained by interview with the parent/legal guardian/participant and from the participant's medical records.
2. Concomitant medications of interest administered within 7 days prior to first study dose and during the period of administration of study drug, including herbal products of interest, will be recorded (see **Appendix II**).
3. Physical examination, including abnormal physical findings, height (measured standing if possible), weight and waist:hip ratio will be obtained (see **Section 6.3 #2**).
4. Safety laboratory testing (see **Section 6.6.1**)
5. PK sampling (see **Section 6.6.2**).

6.2 Screening

Research staff at sites will screen potential participants for eligibility requirements per local institutional policies.

6.3 Enrollment/Baseline

Baseline Assessment (Day 0)

After the parent or legal guardian has provided informed consent /HIPAA, the participant has provided assent (if applicable), and after it has been determined that the participant satisfies all inclusion and no exclusion criteria, the following evaluations will be performed and recorded in the CRF:

1. Participant demographics
2. Physical exam.
NOTE: The initial physical examination information (except the height, weight, and waist/hip measurements) may be obtained from the medical record but must have been performed within 24 hours prior to first study dose. Height, weight and waist/hip measurements must be performed after consent. BMI will be calculated from height and weight using the following formula: $BMI = [\text{weight (kg)} / (\text{stature (cm)})^2] \times 10,000$. Refer to the Centers for Disease Control (CDC) pediatric BMI calculator (<http://apps.nccd.cdc.gov/dnpabmi/>) to determine the BMI percentile. The BMI percentile will be obtained using the BMI calculator and verified using the age- and sex-specific CDC BMI charts (see **Appendix I**).
3. Pertinent medical history
4. Concomitant medications of interest (7 days prior to first dose of study drug) (see **Appendix II**)

5. Laboratory determinations (see **Table 2, Section 6.6.1**)
6. Culture results of blood, urine, sputum, or wound (if obtained as part of routine care) within 72 hours prior to the first dose of study drug
7. For participants receiving clindamycin per routine care, the date and time for the doses administered prior to first dose of study drug will be recorded (up to a maximum of 6 prior doses)
8. Serum pregnancy test (females only who have reached menarche) within 24 hours prior to first dose of study drug.

Assessments/Procedures (Days 1–14)

The participant will start study drug upon completion of the baseline procedures. Standard of care dosing may need to be increased to comply with the protocol; refer to **Section 7.1.2** for specific dosing information. Participants who transition to oral therapy will also participate in the oral-dose PK portion.

The following assessments will begin with the first dose of study drug and continue throughout therapy up to Day 14:

1. Concomitant medications of interest (see **Appendix II**)
2. Start date/time and stop date/time of clindamycin administration and flush date/stop time after IV administration
3. Feeding status (during PO PK portion only): nothing by mouth (NPO), clear liquids, full feeds, etc.
4. Collection of PK samples (including date/time) (see **Section 6.6.2**)
5. Results for laboratory tests of interest (see **Section 6.6.1**)
6. Collection of culture results (if available)
7. Adverse events (see **Section 8.2.1**)

6.4 End of Therapy OR Early Withdrawal/Discontinuation

The following assessments will be conducted at early withdrawal or end of therapy:

1. Concomitant medications of interest (see **Appendix II**)
2. Physical examination
3. Laboratory evaluations (see **Section 6.6.1**)
4. Adverse events (see **Section 8.2.1**)

6.5 Follow-up Safety Phone Call

Assessments/Procedures (Day 3 Post Treatment): This visit will be a phone follow-up unless the participant is still hospitalized, in which case an in-person visit or chart review may be performed. This assessment will occur 3 days (+/- 1 day) after the last dose of study drug (i.e., end of therapy or early withdrawal/discontinuation). The following information will be obtained:

1. Adverse events (see **Section 8.2.1**)
2. Concomitant medications of interest (**Appendix II**)
3. Results for laboratory tests of interest (see **Section 6.6.1**)

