5.2.1 Duration of Study Participation

Duration of therapy will be up to 14 days for children who receive the first dose of IV clindamycin as the study drug. The total duration of therapy with clindamycin will be determined by the treating physician for those children who are receiving clindamycin as part of routine care; however, only 14 days of therapy will be considered as study drug. Study follow-up will occur 3 days (+/- 1 day) after the last dose of study drug. Patients who are receiving antimicrobial agents other than clindamycin may enroll in this study and receive up to 3 doses of IV clindamycin and 4 doses of oral clindamycin in addition to their standard of care therapy. Participants who transition to oral clindamycin may return as outpatients to complete the PK portion of the study.

Total duration of study participation will be up to 18 days. This will comprise a 1-day screening period; a maximum 14-day treatment period; and a 3-day post-study observation period to monitor for serious adverse events. The 3-day post-treatment visit may be a phone follow-up. Patients may continue clindamycin per their physician's recommendation after they have completed participation in this (maximum of) 18-day study.

Figure 2. Timeline

* Minimum of 1 dose of IV clindamycin before IV PK period (see **Section 6.6.2** for further details).

** Minimum of 3 doses of PO clindamycin before PO PK period.

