7.1.2 Dose and Timing

Both q6h and q8h dosing will be allowed for both oral and IV dosing of clindamycin. For children receiving clindamycin as part of clinical care, this protocol will not prescribe a route of administration or dosing interval; the dose, route of administration, and dosing interval prescribed by the treating physician will be recorded on the CRF. However, if the prescribed dose is less than the lowest dose for this study, the dose of clindamycin will be changed to comply with the study dose. Dosing greater than 2.7 g/day will be allowed for children receiving clindamycin as part of clinical care. See **Section 5.2.1** for duration of therapy.

IV dosing: A minimum of 2 study doses of IV clindamycin will be administered. The dose administered will be based on TBW at 30–40 mg/kg/day divided q6h or q8h with a maximum dose of 2.7 grams/day. The drug will be administered over 30 (+/- 5) minutes. The venous access line will be flushed per local practice after completion of IV administration, and the time of the end of flush will be documented. It is preferred that the flush be ≤ 1 minute after the end of infusion.

Oral dosing: For those participants who are receiving clindamycin as a solution, they will receive 30–40 mg/kg/day divided q6h or q8h. For those participants receiving the capsule formulation, they will receive the dose of clindamycin defined in **Appendix III**. Only whole capsules will be used. The oral solution will be used for those participants who cannot swallow capsules. No more than 12 PO study drug doses will be administered as part of this study.

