8 ASSESSMENT OF SAFETY

8.1 Specification of Safety Parameters

AEs will be collected during and after study drug administration and for 3 days following end of therapy with clindamycin. Results will be tabulated by MedDRA System Organ Class and Preferred Term.

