8.2 Methods and Timing for Assessing, Recording, and Analyzing Safety Parameters

AEs will be collected from the time of consent, throughout the period of study drug administration, and for 3 days following end of therapy with clindamycin. See **Section 8.6** for clarification for AEs identified at the 3-day follow-up visit and for serious AEs (SAEs). Safety will be assessed by frequency and incidence of AEs and SAEs. The Best Pharmaceuticals for Children Act (BPCA) safety monitoring committee (DMC) convened by NICHD will review data and safety information from study participants.

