8.2.3 Identification of Events and Timeframe for Reporting

As all participants in this study will have pre-existing medical conditions and may be currently hospitalized, those pre-existing conditions will not be considered as adverse events. New events that occur or pre-existing conditions that worsen in terms of frequency or intensity will be reported as adverse events.

All reportable events as defined above, determined to be an AE based on physical examination, laboratory findings, or other means, will be recorded in the source documents and entered in the CRF. Each event will be recorded on an AE CRF starting after consent has been obtained. The investigator will provide the date of onset and resolution, intensity, action(s) taken, changes in study drug dosing, relationship to study drug, and outcome. Any event beginning more than 3 days after the last dose of study drug will not be captured.

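### The last safety contact may fall on day 2, before the 3-day adverse event window closes, and Section 8 ends that window from two different anchors

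*Supplement*

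**What the plan says.** All references are to the latest protocol version.

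**Timing of the contact.** Section 6.5: "This assessment will occur 3 days (+/- 1 day) after the last dose of study drug". Section 5.2.1 gives the same window: "Study follow-up will occur 3 days (+/- 1 day) after the last dose of study drug". No later contact is scheduled. A parenthesis in 6.5 equates the last study dose with therapy ending or the child leaving the study early. For a child still in hospital, 6.5 allows a visit or a chart review in place of the call.

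**End of adverse event (AE) capture.**
- Section 8.1: "AEs will be collected during and after study drug administration and for 3 days following end of therapy with clindamycin". Section 8.2 has the same end point: "throughout the period of study drug administration, and for 3 days following end of therapy with clindamycin".
- Section 8.2.3: "Any event beginning more than 3 days after the last dose of study drug will not be captured".
- Section 8.2.4 follows ongoing AEs to 3 days after the last study dose. It gives 3 more days (10 for serious events) to events already identified at the last contact.

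**What counts as study drug.** Section 5.2.1 counts at most 14 days of therapy as study drug and lets clindamycin continue afterwards on the physician's advice. Section 7.1.2 adds: "No more than 12 PO study drug doses will be administered as part of this study".

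**Related text.** Section 6.3 and Table 1 schedule AE assessment through Day 14, and Table 1 labels end of therapy as Day 14. Section 4 ends observation 3 days after clindamycin stops, or on day 17/18 for children treated for more than 14 days. The Synopsis and 5.2.1 cap participation at 18 days.

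**The concern.** There are two separate weaknesses in how post-treatment events are found.

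First, the contact can come before the window it serves has closed. An event that starts after a day-2 call but by day 3 is reportable, yet for a discharged child no planned contact remains that would elicit it. The extra follow-up in 8.2.4 does not help, because it applies only to events already known at the contact.

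Second, the window has two anchors. They coincide when clindamycin and study drug stop together. They separate when clindamycin continues past the last study dose, which the protocol foresees. An event in the gap is to be collected under 8.2 and is excluded under 8.2.3.

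Safety is a secondary aim, assessed in 8.2 by frequency and incidence of AEs and serious AEs. In a study of 24 to 32 children, those figures should not depend on when a site happened to call or on which section it followed.

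**Working it through.** **1. The plan's own figure.** Screening 1 day, treatment up to 14 days and observation 3 days: 1 + 14 + 3 = 18 days. This reproduces the stated maximum. With the tolerance of 1 day either way, the total runs from 1 + 14 + 2 = 17 to 1 + 14 + 4 = 19 days, so a compliant day-4 contact already exceeds 18.

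**2. Share of the window covered.** Covered share = min(contact day, 3) / 3.

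| Contact day | Covered | Left without a scheduled contact |
|---|---|---|
| 2 | 2/3 | 1 day: (72 − 48)/72 = 33% |
| 3 | 3/3 | none |
| 4 | 3/3 | none |

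The 33% is a share of time, not of events, and takes day 2 as exactly 48 hours.

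**3. What it could mean in events.** The documents give no AE rate. Assume that 5% to 30% of children have a new event in the 3-day window, that onset is uniform over it, and that every contact is on day 2 with nothing learned afterwards. The expected number starting after the contact is N × p / 3:
- N = 24: 24 × 0.05 / 3 = 0.4, to 24 × 0.30 / 3 = 2.4.
- N = 32: 32 × 0.05 / 3 = 0.5, to 32 × 0.30 / 3 = 3.2.

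Under those rates this is an upper bound, since not every contact will be early.

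**4. The two anchors.** Twelve oral doses last 12 × 6 h = 3 days (q6h) or 12 × 8 h = 4 days (q8h). As an illustration, assume an oral switch on day 3, q8h dosing, and clindamycin continued to day 14. Oral study dosing then ends about day 3 + 4 = 7.

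| Source | Result for this child |
|---|---|
| 8.2.3 | onset cut-off at day 7 + 3 = 10 |
| 6.5 | contact between day 7 + 2 = 9 and day 7 + 4 = 11 |
| 6.3 and Table 1 | AE assessment through Day 14 |
| 8.1 and 8.2 | capture to day 14 + 3 = 17 |
| Section 4 | observation to day 14 + 3 = 17 |

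The two capture rules end 17 − 10 = 7 days apart. The difference shrinks with a later switch and is zero when clindamycin stops with study drug.

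**5. Does other text settle the anchor?** Only in part. For a child treated beyond 14 days, Section 4, the parenthesis in 6.5 and the Day 14 label in Table 1 all point to the end of study drug, so the literal wording of 8.1 and 8.2 is the outlier. For a child who passes oral dose 12 earlier and stops clindamycin by day 14, Section 4 agrees with 8.1 and 8.2 and disagrees with 8.2.3, and the equation in the 6.5 parenthesis is not true. Section 8.2 sends the reader to 8.6 for clarification, but 8.6 refers back to 8.2.4.

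**The case against.** The strongest reply is that the loss is possible, not built in. Day 3 is the nominal time, an early call is allowed but not required, and a call on day 3 or 4 covers everything. Day-3 onsets stay reportable if they come to light, and 8.2.3 accepts identification by examination, laboratory findings or other means. Children still in hospital can be seen or have their charts reviewed, and laboratory results are collected until about the same time. All of this stands. It confines the first weakness to discharged children who are called early.

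A reader might infer that post-treatment events are missed by rule, or that AEs are systematically under-counted. The documents support neither, because nothing in them says how often calls would be early. Nor do they support a claim that late rash or diarrhoea in particular would be lost: Section 2.3.1 lists reactions without onset times.

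On the anchors, the reply is that 6.5, Table 1, Section 4 and the 14-day rule in 6.6.1 point to one working meaning. That largely holds beyond day 14, but not for the child who finishes the oral study doses sooner. A reader might also take the 7-day difference as 7 days without AE assessment. It is not: 6.3 and Table 1 keep assessment going to Day 14. It is a conflict between rules about which events count.

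**Conclusion.** Both weaknesses are present in the latest version, at modest size. A compliant contact on day 2 leaves up to one third of the 3-day window unascertained in discharged children who are called early. On assumed event rates of 5% to 30% and every contact on day 2, that is at most about 0.4 to 2.4 events among 24 children. The actual number depends on call timing and AE rates that the documents do not give.

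The anchor conflict applies only where clindamycin continues past oral study dose 12 or day 14. There the same event can be both collectable and excluded. It is sharpest for the child who passes oral dose 12 well before clindamycin ends.

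The effect is limited to the completeness and consistency of the secondary safety outcome. The primary PK outcome is untouched. The point merits an amendment because the remedy is short and the cohort is small enough for one or two events to show.

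**What to change.** - **Sections 5.2.1 and 6.5:** set the contact no earlier than the end of the AE window, for example 3 days with a tolerance of −0/+1 day, and have the caller ask about any onset through day 3.
- **Sections 8.1, 8.2, 8.2.3 and 8.2.4:** use one anchor, consistent with Section 4, 6.3, 6.5 and Table 1. State how clindamycin taken after oral study dose 12 is treated for AE capture. Section 5.2.1 already settles that therapy beyond 14 days is not study drug.
- **Synopsis and 5.2.1:** reconcile a day-4 contact (19 days) with the 18-day maximum.

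Table 1 carries no tolerance for the call. The similar phrase in 6.6.1 closes a laboratory interval and can stay.

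The cost is amendment wording and an allowed contact range of day 3 to 4 in place of day 2 to 4, so a few more calls will fall out of window. An earlier protocol version in the same supplement required contact at 72 to 96 hours, so such a window has already been specified for this study.

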6.6 Laboratory Evaluations

6.6.1 Clinical Laboratory Evaluations

Laboratory testing (**Table 2**) will be collected on all participants and be performed in the local laboratory at each site. Laboratory values will be collected within 72 hours prior to the first dose of study drug through 3 days (+/- 1 day) after the last dose of study drug. If multiple values for a laboratory are obtained in the 72 hours prior to start of first study dose, record the value closest to the start of first study dose. Laboratory values performed as part of routine care within 72 hours prior to the first dose of study drug may be used for baseline laboratory tests. Laboratory values will also be obtained at the end of therapy. Laboratory values obtained within ± 24 hours of discontinuation of study drug or within ± 24 hours of completion of 14 days of study drug (if participant is continuing clindamycin beyond 14 days) may be used as end-of-treatment laboratory values. If the baseline and end of therapy laboratory tests have not been performed as part of routine care, they will be performed for the study per the protocol schedule. The serum pregnancy test will also be performed at the local laboratory. Alpha (α)-1-glycoprotein will be measured from one of the PK samples by the central laboratory once during the study using an ELISA kit (central laboratory). Sites do not need to collect an extra sample to measure α -1-glycoprotein.

Table 2. Laboratory Evaluations

Hematology	Serum Biochemistry
Hemoglobin	Sodium
Hematocrit	Potassium
Platelets	Chloride
White blood cells	Bicarbonate
	Total calcium
	Glucose
	Creatinine
	Blood urea nitrogen
	Total protein
	Albumin
	Aspartate aminotransferase
	Alanine aminotransferase
	Bilirubin

6.6.2 Special Assays or Procedures

PK Samples

Blood (0.5 mL) will be collected with scheduled IV and oral doses of clindamycin for clindamycin plasma concentration determinations (see **Table 3** below for schedule). In participants receiving IV clindamycin, PK samples should be collected from a site separate from the site of administration.

PK samples (#1-6) will be obtained at any point after the first study dose. For PO clindamycin, PK samples will begin with any dose after the 3rd dose of PO study drug (first PK sample obtained within 15 minutes prior to PO study dose #4 or later).

However, if each of the following criteria are met, PK samples (1-6) can be obtained at any point after consent:

- The most recent pre-consent standard of care dose is the same dose/interval/route as post-consent on-study doses
- Exact start and stop times of the pre-consent dose are clearly documented (estimated times are not acceptable), AND
- Exact flush time of the pre-consent dose is clearly documented. Estimated flush times are not acceptable unless there is documentation of site standards for infusion/flush periods.

The PK samples will be drawn according to the following schedule relative to the end of flush (IV PK) or actual time of oral administration (PO PK).

Table 3. PK Schedule

PK Sample	Scheduled PK Sampling Times				
	Time (Hours)*	IV Dose*		PO Dose	
		Q6h	Q8h	Q6h	Q8h
1	Pre-dose 0 (within 15 minutes prior to the dose)	X**	X**	X**	X**
2	0.5 (± 5 minutes)	X**	X**	N/A	N/A
3	1–1.5	X	X	X**	X**
4	3–4	X**	X**	X**	--
5	5–6	--	X	--	X**
6	Pre-dose (will depend if on q6h or q8h dose schedule)	X**	X**	X**	X**
Total number of samples		5	6	4	4

* Time starts at end of flush after the 30-minute infusion.

** Priority samples (see paragraph below).

Every effort should be made to collect all PK samples for each participant. Collection of PK samples should be timed with collection of laboratory tests per standard of care to minimize blood draws specifically for the study. If it is impractical to collect all PK samples during the same dosing interval, samples can be obtained at different dosing intervals. If it is impossible to obtain all PK samples for each participant, **PK samples can be prioritized to include:**

- a) **For IV administration: pre-dose, 0.5 hours, 3–4 hours, and pre-next dose**
- b) **For oral administration: pre-dose, 1–1.5 hours, 3–4 hours (q6h dosing), 5–6 hours (q8h dosing), and pre-next dose**

Clindamycin concentrations in plasma will be measured at a central laboratory using a validated bioanalytical assay. In addition, scavenged samples will be obtained.

Scavenged Plasma Sampling

Plasma samples collected in EDTA tubes during the course of therapy (~100 µL plasma or ~200 µL whole blood) will be procured, after consent. A maximum of 10 scavenged plasma samples will be collected per participant. Collection may begin with any specimen collected after the first dose of study drug through 24 hours after the last dose of study drug. The date and time of sample collection, as well as the date and time the sample is frozen, will be collected for all scavenged samples.

Minimizing Blood Loss

To minimize the amount of blood sampling, laboratory values will be obtained only at baseline and end of study. If they have been obtained as part of routine care within 72 hours prior to first dose of study drug, the baseline laboratory values do not need to be repeated. The PK sampling scheme will be employed such that no more than a total of 8 mL (< 3 mL/kg) of blood is obtained from each participant for PK analysis. Plasma samples will be collected in 0.5 mL blood aliquots.

